Aim 2: Evaluate the impact of home-based TeleNP on the differential diagnosis of typical and atypical AD. 2a. Is the neuropsychologist's diagnosis comparable across TeleNP and FF conditions? 2b. Does flexibility to incorporate additional tests (Flexible Assessment) that are not readily adaptable to video administration alter diagnostic conclusions? *Given that neuropsychologists' conceptualizations of patient presentations may differ from the referring neurologist, this Aim will appraise whether TeleNP results in the same diagnoses from neuropsychologists compared to FF (gold standard) conditions.*

Aim 3: Appraise the feasibility and acceptability of TeleNP in the evaluation of AD patients. 3a. What is the user experience of TeleNP by patients, care partners, neuropsychologists, and psychometrists? 3b. Are there barriers or unique benefits of TeleNP that may influence future use and scalability in clinical care? *This Aim will utilize mixed methods, including interviews about the user experience and surveys of intervention feasibility and acceptability, to address quantitative and qualitative aspects of TeleNP that may influence the pragmatic implementation of remote assessments in a future, definitive trial.*

II. Background and Significance:

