Aim 2: Equivalence of Neuropsychologist's Diagnosis: *Considering that neuropsychologists' conceptualizations of patient presentations may differ from the referring neurologist, the goal of this Aim is to appraise whether TeleNP results in the same diagnoses from neuropsychologists compared to FF (gold standard) conditions, and determine whether inclusion of flexibility to incorporate additional tests (Flexible Assessment) that are not readily adaptable to video administration alters diagnostic considerations.* Neuropsychologist-determined diagnosis (i.e., typical AD, atypical/complex AD, not AD) and severity (i.e., subjective concerns; MCI; dementia) will be assessed immediately after the standard protocol via a REDCap survey. To clarify whether the Flexible Assessment alters the neuropsychologists' conceptualizations, neuropsychologist diagnosis and severity will also be documented after the Flexible Assessment is completed.

Aim 3: Feasibility and Acceptability of TeleNP: *This Aim will utilize mixed methods, including patient, care partner, neuropsychologist, and psychometrist interviews about the user experience and surveys of intervention feasibility and acceptability (i.e., modified UTAUT), to address quantitative and qualitative aspects of TeleNP that may influence the pragmatic implementation of remote assessments in a future, definitive trial.*

Qualitative:

- Patients and Care Partners: **A subset of diverse patients (n=20) and any associated care partners** will be invited to participate in semi-structured interviews with the psychometrist within one week of completing both FF and TeleNP conditions. We will sample for diverse perspectives, including participants from both genders and typical vs. atypical AD. These interviews will focus on the participant's user experience, guided by

UTAUT domains and specific attention to home setting and potential care partner involvement.

- Psychometrist and Neuropsychologists: The psychometrist and neuropsychologists will also participate in brief, separate interviews to garner information regarding feasibility, acceptability, and strengths/weaknesses of TeleNP; these interviews will be conducted by [name] on four occasions, with each interview occurring after completion of 20 study visits.

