Quantitative: To appraise feasibility of TeleNP, we will include measures of enrollment tracking (i.e., enrolled vs. decline), protocol assessment time, tracking of protocol adherence (i.e., completion of Core Battery), and presence of technological difficulties (e.g., termination of assessment due to technological difficulties). **The psychometrist will ask all patients (n=80) and associated care partners (up to n=80)** to complete validated 4-item Acceptability and Feasibility of Intervention Measures^{32, 33} after both conditions, and a 19-item UTAUT questionnaire (adapted to TeleNP) after the TeleNP condition to measure determinants of intention to use.

We will document the fidelity of assessment administration and scoring using a fidelity checklist in a random 20% sample of participants.

Costs and Payments

All costs associated with the implementation and maintenance of the study shall be supported by [name] grants. There is no charge to participants or participants' insurance for participation.

Clinical Trial participants will receive \$25 to compensate for their time after both visits are completed. Care partners will not be compensated.

C. Description, Risks and Justification of Procedures and Data Collection Tools:

Description of Risks:

Potential risks to participants, by intervention, including physical, psychological, social, cultural, financial, and legal risks: For both conditions, there are no expected physical or legal risks. Participants will be advised that the clinical trial is voluntary, and that they may obtain a clinical neuropsychological evaluation in lieu of the research study as part of standard of care.

Risks associated with neuropsychological assessments:

- Both conditions (FF [control] and TeleNP [intervention]): The potential risks associated with participation in the study are minimal and include the risk of anxiety and/or fatigue, boredom or frustration during the completion of the neuropsychological testing sessions. An additional potential risk is loss of confidentiality, which could lead to potential social or cultural risks, if personal sensitive information is shared outside of the intervention.
- TeleNP: For the TeleNP condition, there are no expected physical, social, cultural, financial or legal risks. One potential risk is loss of privacy and/or confidentiality, as described below. We will employ video-based assessments for the TeleNP section, using HIPAA-compliant platforms.

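### Aim 3b asks about barriers to TeleNP, but patient and care partner interviews are tied to completing both conditions, so those who withdraw or never complete TeleNP give no first-hand account

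*Combined protocol and SAP*

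**What the plan says.** Specific Aims, Aim 3b, asks: "Are there barriers or unique benefits of TeleNP that may influence future use and scalability in clinical care".

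IV.C Outcome Measure(s), Aim 3, describes these sources:

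- **Patient and care partner interviews.** The sample is "A subset of diverse patients (n=20) and any associated care partners", interviewed "within one week of completing both FF and TeleNP conditions". On selection, the plan says: "We will sample for diverse perspectives, including participants from both genders and typical vs. atypical AD".
- **Staff interviews.** The psychometrist and neuropsychologists are interviewed "on four occasions, with each interview occurring after completion of 20 study visits".
- **Tracking.** The plan records "measures of enrollment tracking (i.e., enrolled vs. decline"), assessment time, completion of the Core Battery, and "presence of technological difficulties (e.g., termination of assessment due to technological difficulties").
- **Surveys.** "The psychometrist will ask all patients (n=80) and associated care partners (up to n=80") for the 4-item acceptability and feasibility measures after both conditions, and for the 19-item UTAUT after TeleNP.

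Section IV.E adds that technical problems are tracked during the study and discussed at monthly team meetings. Section IV.F triangulates the interviews with the feasibility data and summarizes feasibility and acceptability by modality.

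Withdrawal is allowed at any time (IV.A), and the enrollment ceiling covers screen failures and withdrawals together. The documents describe no exit interview and no record of why a patient withdrew or declined.

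**The concern.** A study of barriers needs to hear from the people whom the barriers stopped. Here the condition for being interviewed is that both assessments were completed, one of them the TeleNP session at home. Background and Preliminary Studies stress that the new setting is the home without on-site staff, and a care partner is encouraged but not required. Patients who could not manage in that setting hold the most direct evidence on Aim 3b, and they are the ones most likely to fall outside the interviews.

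At stake is the content of the qualitative themes. The pilot is meant to prepare a definitive multi-clinic trial. If the themes come only from people for whom both visits worked, barriers will tend to look fewer and milder than they are. The planned triangulation would then pair a count of failures with no account from the patients who failed. Such accounts are hard to recover after those patients have left.

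**Working it through.** The plan gives no rationale for 20 interviews, no non-completion rate and no calculation for Aim 3, so there is no stated figure to reproduce. The check has three parts.

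**1. What each kind of patient can contribute under the text as written**

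| Patient | Interview | UTAUT | 4-item measures | Other trace |
|---|---|---|---|---|
| Completes both visits | Eligible | Yes | Yes | Tracking, staff |
| TeleNP first, withdraws before FF | No | Yes | TeleNP ratings only if given after each condition | Tracking, staff |
| FF first, withdraws before TeleNP | No | No | FF ratings only if given after each condition | Tracking, staff |
| TeleNP session stopped early | Depends on what counts as completing | Probably, not stated | Not stated | Termination tracked, staff |
| Declines enrollment | No | No | No | Counted as a decline |

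Two ambiguities affect the table. First, completing a condition is not defined, and the Core Battery need not be given in full (IV.B, Data Collection), so a partial session might qualify. Second, the timing of the 4-item measures can mean after each condition or once both are done. The by-modality summary in IV.F favors the first reading. On either reading, rows two and three give no interview.

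**2. What the rule does to the 20 interviews**

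Inputs from the documents: N = 80 patients and n = 20 interviews, so 20/80 = 25% are interviewed. Assumption: a non-completion rate d, giving k = 80d non-completers.

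- Expected non-completers if the 20 were drawn at random from all 80: 20 × k/80.
- Chance of at least one: 1 − C(80 − k, 20)/C(80, 20).

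| d (assumed) | k | Expected among 20 | Chance of at least one | Current rule |
|---|---|---|---|---|
| 5% | 4 | 1.0 | 0.69 | 0 |
| 10% | 8 | 2.0 | 0.91 | 0 |
| 20% | 16 | 4.0 | 0.99 | 0 |
| 30% | 24 | 6.0 | >0.99 | 0 |

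Random drawing serves only as a benchmark, because the actual sampling is purposive. The zero in the last column follows from the rule at every rate, with non-completer meaning anyone who does not meet the plan's completion condition.

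**3. Staff interviews**

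Four interviews at steps of 20 reach 4 × 20 = 80. If the unit is a participant, that covers 80/80. If it is a single-modality visit, there are 80 × 2 = 160 visits, and the last interview falls at 80/160 = 50% of them. The text does not settle which is meant.

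**The case against.** The strongest defense is that the qualitative analysis seeks views of TeleNP compared with FF (IV.F), and only someone who has had both can compare them. That is a sound reason to interview completers. It does not explain why nobody else is interviewed, since Aim 3b asks about barriers as well as comparison.

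A reader might infer that those who fail are never heard at all. The documents do not support that. Declines, Core Battery completion and technical terminations are tracked, and technical issues go to monthly meetings. The psychometrist, who runs the test call and the battery, is interviewed about feasibility and weaknesses. A TeleNP-first patient can answer the UTAUT before withdrawing. What is missing is the patient's own account and the reason for stopping.

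Three other strong readings also go too far:

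- **Sampling on gender and diagnosis only.** The two factors are introduced as examples, so others may be used. Completion still decides who can be invited.
- **A terminated session always excludes the patient.** Completion is undefined, so a partial session might count. Exclusion is clear for those who withdraw or never have a TeleNP session.
- **Staff interviews miss half the study.** That holds only if the unit is a single-modality visit. The product of 80 matches the number of participants equally well.

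It is also fair to say that Aim 3 is exploratory, that its measures are descriptive, and that no equivalence conclusion in Aims 1 or 2 depends on it. That limits the weight of the point without removing it.

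**Conclusion.** The concern holds in a limited form. No first-hand interview is planned for patients who withdraw or never complete TeleNP, nor for their care partners, and no reason for stopping is recorded. Because the interview rule is tied to overcoming the barriers that Aim 3b asks about, the themes would tend to understate them.

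The size of that understatement cannot be derived from the documents. The only figures available are the interview counts: 2-4 non-completers expected among 20 at an assumed 10-20% non-completion, against 0 now. Any figure for a shift in mean acceptability would need invented scores for both groups, so none is given.

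The change is worth making before interviews begin, since the pilot's purpose is to inform a larger trial. The staff-interview wording is a separate matter of clarification and is not evidence of bias.

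**What to change.** Keep the 20 patient interviews and amend IV.C (Aim 3) and IV.F as follows:

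1. Make any patient who reached the TeleNP pre-visit call, and that patient's care partner, eligible for interview within one week of completing both visits or of stopping, where they agree to be contacted.
2. Add completion status and technical failure to the purposive sampling factors, without a fixed quota.
3. When a patient who has started TeleNP stops, offer the 4-item measures for TeleNP and the UTAUT at that point.
4. Report ratings for all who started TeleNP beside those for completers.
5. As a clarification, state whether the 20 study visits between staff interviews are participants or single-modality visits, so that the four interviews span the whole study.

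**Cost.** The number of interviews and the staff stay the same. The consent wording must allow contact after stopping, which needs ethics review. Some who withdraw will refuse. Those who had only one modality cannot compare the two, so their interviews inform barriers only. Each such interview takes a place from a completer, and ratings may look slightly less favorable. Patients who decline enrollment, or leave before the TeleNP pre-visit call, remain outside the interviews.

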The overarching goal of this proposal is to a) assess the feasibility and preliminary validity of **home-based delivery of TeleNP** to patients with suspected AD, referred for cognitive assessments in a Neurology Clinic; and b) elucidate whether TeleNP is equivalent to face-to-face evaluation (FF) for diagnostic adjudication of atypical versus typical AD. To accomplish these goals, we will conduct a **pilot clinical trial** of two testing modalities, TeleNP versus FF, for delivery of neuropsychological evaluations. Neurologist-referred patients with typical (i.e., memory-predominant; n=40) and atypical (i.e., complex and/or non-memory predominant; n=40) presentations of *possible* AD will be enrolled in the study. Care partners of participants will also be consented to the study and included in stakeholder surveys/interviews. Using a cross-over design, all participants will undergo evaluations (clinical interview + Core Battery of cognitive tests) in both modalities, approximately 4-6 weeks apart to account for potential practice effects. Although all participants will be referred due to suspected AD, the neuropsychologist will be blinded to the specific diagnosis (i.e. typical versus atypical) from the neurologist. The Core Battery will include measures of memory, executive, visuospatial, and language functions. To further minimize practice effects, alternate assessment forms will be implemented and order of test forms will be counterbalanced. Some tests are not readily adaptable to video-based delivery due to tactile/physical stimuli; as such, we will assess whether a Flexible Assessment (i.e., option to include additional tests, after completion of Core Battery) in the FF modality alters diagnostic conclusions. Finally, in an exploratory aim, we will identify stakeholder perspectives of TeleNP that inform pragmatic implementation of remote neuropsychological evaluations. Our Aims are:

Aim 1: Determine the validity of home-based video administration of neuropsychological tests (TeleNP) for assessing AD. 1a: Are cognitive test results equivalent across TeleNP and FF conditions in patients with suspected AD? 1b. Is this equivalence consistent across referral diagnoses (i.e., Typical vs. Atypical AD)? *This Aim will test the validity of cognitive measures assessed with TeleNP and determine whether the validity of TeleNP differs based on referral diagnosis.*

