To overcome these significant gaps in prior research, we propose to demonstrate the feasibility and validity of home-based, comprehensive TeleNP. We will conduct a cross-over pilot trial to evaluate the feasibility and preliminary validity of standard, face-to-face (FF) neuropsychological assessment versus home-based video TeleNP in adults with suspected typical or atypical AD. germane to the generalizability of TeleNP to clinical settings, the trial will be embedded in the University of Colorado Hospital (UCH) Memory Disorders Clinic, which will further facilitate an appraisal of whether TeleNP assessments are appropriate for diagnostic adjudication of typical vs. atypical ADRD phenotypes. In an exploratory aim, we will utilize a mixed methods approach to assess the feasibility and acceptability of TeleNP among key stakeholders: patients, their care partners, neuropsychologists, and a psychometrist. This approach will be guided by the Unified Theory of Acceptance and Use of Technology (UTAUT) model; this theoretical framework identifies “social influence” and “facilitating conditions”, which can assess the potential influence of the home environment on user acceptance and intentions to use.¹⁶ This pilot clinical trial will delineate the feasibility of implementing TeleNP in a Neurology clinic setting and thereby prepare us for a future definitive pragmatic trial of TeleNP effectiveness across multiple clinics.

III. Preliminary Studies/Progress Report:

This is an NIH-funded R21 application with no current pilot data. There are published studies of telehealth and neuropsychology; however, the vast majority of studies using remote neuropsychological testing have been delivery of services to another health care facility, with the presence of on-site support to the patient^{8, 9, 17-20}. Although those studies emulated a “controlled” setting of a clinic, they did not address the feasibility of implementing TeleNP in a more real-world context, when the patient is at home with no staff support. **Whether due to rural-based access to care barriers, functional limitations, or COVID-19, many older patients have limited access to remote clinic offices for evaluation**, hence raising questions regarding scalability of clinic-to-remote clinic neuropsychological assessments. As such, we will appraise the feasibility and preliminary validity of TeleNP as a comprehensive neuropsychological assessment via home-based video telehealth administration.

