For Aim 3, Feasibility and Acceptability of Intervention Measures and the UTAUT will be analyzed descriptively with means and interquartile ranges. Analysis of qualitative data will be a continuous process beginning with initial interviews and continuing throughout the data generation period. All interviews will be audio-recorded and transcribed verbatim. Directed by [name], rapid qualitative analysis³⁶ will be used to understand multiple user perspectives on feasibility, acceptability, and other potential factors affecting use, including home context, of TeleNP compared to FF. At least 2 team members will analyze transcripts.³⁷ All data will be entered into ATLAS.ti v8.0 (GmbH, Berlin) for data management. Transcripts will be analyzed to develop the major themes or concepts reported by interviewees. Using the quantitative and qualitative data, we will conduct sequential mixed methods analyses using data from Aim 3.³⁸ The synthesis stage of data analysis involves triangulating the findings from interviews and quantitative data related to feasibility (i.e., assessment time, protocol adherence, technical issues, etc.), acceptability ratings, availability of a care partner, etc. We will interpret and summarize feasibility and acceptability for each modality from the different user perspective

G. Summarize Knowledge to be Gained:

Appraisal of the feasibility and validity of TeleNP in patients with complex AD presentations will provide a critical platform for the future development of a pragmatic, multi-site trial. Validation of TeleNP in a real-world setting will further increase access to neuropsychological evaluations and reduce patient burden. Specific knowledge to be gained includes:

- Comparison of two testing modalities for neuropsychology: telehealth and standard, face-to-face assessment
- Comparison of diagnostic adjudication for these two neuropsychology modalities
- Test- and interview-specific differences in feasibility and validity in these two modalities

- Qualitative information regarding feasibility, participant experience and acceptability, care partner experience and acceptability, and psychometrist & neuropsychologist experience.
- Greater understanding of technological concerns that may arise in telehealth
- Preliminary understanding of potential benefits of telehealth, both qualitatively and quantitatively

H. References:

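### The UTAUT is meant to measure what determines intention to use TeleNP, but its only stated statistical analysis, means and interquartile ranges, cannot show association with intention

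*Combined protocol and SAP*

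**What the plan says.** **Purpose.** Section IV.C (Aim 3, Quantitative) states who receives the questionnaire: "The psychometrist will ask all patients (n=80) and associated care partners (up to n=80"). It is a "19-item UTAUT questionnaire (adapted to TeleNP) after the TeleNP condition to measure determinants of intention to use". Section II (Background and Significance) introduces the UTAUT model as the guide for the mixed-methods work. It names social influence and facilitating conditions as constructs "which can assess the potential influence of the home environment on user acceptance and intentions to use". Aim 3b in section I asks: "Are there barriers or unique benefits of TeleNP that may influence future use and scalability in clinical care".

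**Analysis.** Section F (Aim 3) says: "Feasibility and Acceptability of Intervention Measures and the UTAUT will be analyzed descriptively with means and interquartile ranges". It then adds that "we will conduct sequential mixed methods analyses using data from Aim 3", and that "The synthesis stage of data analysis involves triangulating the findings from interviews and quantitative data related to feasibility", together with acceptability ratings and care partner availability.

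**Not stated.** No section plans a correlation, model or cross-tabulation of UTAUT constructs against intention. The documents do not list the 19 items, say how they are scored into constructs, or say whether one of the scores is intention to use.

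**Status.** Section I describes the work as exploratory: "in an exploratory aim, we will identify stakeholder perspectives of TeleNP that inform pragmatic implementation of remote neuropsychological evaluations".

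**The concern.** A determinant is a relation: people who differ on the factor should differ in their intention. A mean and an interquartile range describe one score at a time. A construct can score low on average and be unrelated to intention. It can also score high on average and still separate the willing from the unwilling. So the stated statistics cannot serve the stated purpose of the questionnaire.

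What is at stake is limited. The pilot is meant to prepare a definitive trial, and knowing which constructs go with willingness to use TeleNP would help to design it. The questionnaire is the one Aim 3 instrument that puts these constructs to every patient and available care partner, and as planned it would contribute only score levels to that question.

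**Working it through.** The documents give no sample size, power or precision figure for the UTAUT or Aim 3, so there is nothing to reproduce. Two checks were made.

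**1. Do means and interquartile ranges carry information on association?** Two fixed sets of 80 made-up scores on a 1-to-5 scale, one for a construct and one for intention, were paired in three ways. Only the pairing changed.

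| Pairing | Construct: mean (quartiles) | Intention: mean (quartiles) | Correlation |
|---|---|---|---|
| Same order | 3.53 (3.25 to 4.00) | 3.27 (2.67 to 3.75) | 0.98 |
| Random order | 3.53 (3.25 to 4.00) | 3.27 (2.67 to 3.75) | -0.09 |
| Reverse order | 3.53 (3.25 to 4.00) | 3.27 (2.67 to 3.75) | -0.97 |

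The planned summary is identical in all three rows, while the correlation runs from almost perfectly positive to almost perfectly negative. The summary therefore says nothing about association.

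**2. What could a correlation show with the planned numbers?**

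Inputs from section IV.C: 80 patients and up to 80 care partners. These are people who will be asked, not completers. Assumptions: an observed correlation of 0.30 for illustration, a 95% interval, and for the detectable value a two-sided 5% level with 80% power and no multiplicity adjustment.

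Formulas (Fisher z): SE = 1/√(n − 3); interval = tanh(atanh(r) ± 1.96 × SE); detectable r = tanh((1.96 + 0.84) × SE).

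With n = 80:
- SE = 1/√77 = 0.114, and atanh(0.30) = 0.310.
- Limits on the z scale: 0.310 ± 1.96 × 0.114, which is 0.086 to 0.533.
- Back-transformed: 0.09 to 0.49.
- Detectable r = tanh(2.80 × 0.114) = 0.31.

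With fewer respondents (assumed, except that 40 is also the size of one referral group):

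| n | 95% interval for r = 0.30 | Detectable r |
|---|---|---|
| 80 | 0.09 to 0.49 | 0.31 |
| 72 | 0.07 to 0.50 | 0.33 (0.325) |
| 64 | 0.06 to 0.51 | 0.34 |
| 40 | -0.01 to 0.56 | 0.43 |

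The standard error is the one for a Pearson correlation. A Spearman interval would be slightly wider, so these figures are approximate. They apply to single correlations, not to a multivariable model, whose number of predictors is unknown.

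**The case against.** The strongest reply is that the plan never promised an association. Measuring determinants can mean recording the level of factors that the UTAUT framework already identifies, and descriptive summaries do that. The sentence in section II concerns the model guiding the whole mixed-methods approach, not the statistics of the questionnaire. Aim 3b states no association hypothesis. This reading is possible. Still, section II and Aim 3b both speak of influence on use, which favours the relational reading. If levels were all that was meant, section IV.C should say so.

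A reader might infer that Aim 3b will yield no information on what affects use, or that the synthesis rests on score levels alone. The documents do not support that. Section IV.C has the interviews follow UTAUT domains, with attention to the home setting and care partner involvement. Section F analyses them for factors affecting use and triangulates them with feasibility data, acceptability ratings and care partner availability. The question therefore has a qualitative method. What is missing is narrower: an estimate of association in the full sample. The interviews cover about 20 patients and any associated care partners, and they can suggest reasons but not estimate association across all respondents.

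Two further cautions stand. It is tempting to assume that the data for the association are certain to exist, but an intention score among the 19 items is an assumption. It is also tempting to expect correlations to reveal what drives use. Answers from one questionnaire at one time cannot do that.

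Finally, description is a defensible choice in an exploratory pilot aim with no UTAUT hypothesis or threshold. That limits the weight of the point but does not remove the mismatch between purpose and analysis.

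**Conclusion.** The point holds in a limited form. The UTAUT is collected to measure determinants of intention to use, and its only stated statistical analysis cannot show whether any construct is associated with intention. The qualitative work partly covers the same question, but in a subset and without an estimate.

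An added analysis would be informative though imprecise: at 80 respondents a correlation of 0.30 would be known to within about 0.09 to 0.49, and at 40 the interval would include zero. This rests on near-complete response, on construct scores that can be formed from the adapted items, and on an intention score being among them.

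The point is minor. It lies within an exploratory aim of a pilot and leaves Aims 1 and 2 untouched.

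**What to change.** In section F (Aim 3):

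- State how the 19 items are scored into constructs, and confirm whether they include an intention-to-use score. If they do not, use the acceptability measure as the outcome and describe the result as association with acceptability.
- Report exploratory Spearman correlations of each construct with intention, with 95% confidence intervals. Do this separately for patients and care partners, since the two are paired and should not be pooled as independent respondents.
- In patients only, also compare intention by care partner availability. Among care partners availability is constant, so it cannot be examined there.
- Treat any multivariable model as secondary.
- Keep the means and interquartile ranges as description, and carry the new estimates into the mixed-methods synthesis.

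If the sponsor intends only to record construct levels, rewording the purpose in section IV.C would remove the inconsistency, but the full-sample question would stay unanswered.

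**Cost.** A few lines of plan text and a short analysis of data already being collected, with no new visit, respondent or questionnaire. The downside is several cross-sectional exploratory estimates without multiplicity control, which should be labelled as such and not read as causal. If most respondents score high, the limited spread will also make the correlations harder to interpret.
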